5d Clinical trial site (NUNM) Principal Investigator is [name]. [name] team will consist of three co-Investigators, [name], ND, MS a clinical research-trained, licensed physician who has previously recruited participants with CD at NUNM; [name], PhD a clinical research-trained toxicologist; [name], ND, MS, LAc a licensed physician and acupuncturist, who participated as a Clinical Investigator in the phase I portion of this trial; and [name], PhD, a biochemist and molecular biologist at OHSU. In addition, [name], PhD, a post-doctoral fellow trained as a biomedical and neuro-scientist, will also assist with the study. The study team also includes [name], a certified phlebotomist and seasoned clinical trials coordinator, [name], PhD, DSOM, an experienced clinical trials coordinator.

[name] will be the responsible party for all clinical trial operations and regulatory requirements. He will oversee the day-to-day operations of the clinical trial. [name] will oversee [name], [name], and [name] in the day-to-day operations of the trial, including collection, processing and storage of all biospecimens. [name] will also assist with all reporting requirements to the sponsor, IRB, and FDA.

[name] will coordinate efforts with the OSU and PNNL co-PIs to finalize all protocol details, sample collection requirements, storage requirements and shipping details, prior to initiation of participant recruitment.

Introduction

6a Background and rationale

The Centers for Disease Control and Prevention estimates 1.3% of U.S. adults (3 million) are diagnosed with Inflammatory Bowel Disease (IBD), and the prevalence of the disease is increasing.¹ Crohn's Disease (CD) is the most prevalent form of IBD, characterized by predominantly small bowel inflammation (although up to 50% may also have colitis), including inflammation in the ileum. CD causes significant symptoms including diarrhea, abdominal pain, bleeding, micronutrient malabsorption, iron deficiency anemia, increased risk of colon cancer, and unintended weight loss. Medical therapy for CD is problematic and no treatment has consistently delivered success in the treatment of CD due to the episodic nature and variability in abnormality.

Protocol

Current treatments are costly, and associated with adverse outcomes including increased risk of lymphoma and infections.²

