6b Choice of Comparator: Control participants will receive placebo capsules containing 288 mg of rice protein (California Natural Products, Lathrop, CA), 109.3 mg microcrystalline cellulose (Stauber USA, Fullerton, CA), 4.3 mg Aerosil® 200 fumed silica (Vivion Inc., San Carlos, CA), and 4.3 mg magnesium stearate (Nitika Pharmaceutical Specialties, Maharashtra, India), and formulated into a capsule by Metagenics, Inc. (Gig Harbor, WA).

7 Objectives

A methodological limitation of assessing the efficacy of CD treatments is that the gut microbiome of CD subjects is highly personalized in terms of state and dynamics. By correlating time-resolved fluctuations in the gut microbiome of CD subjects with their concomitant changes in the profile of XN metabolites, BA profiles, and other markers of gut microbiome-associated biochemical activity as well as with established surrogate end-points of the disease, we hypothesize:

1) XN at the given dose will be safe and tolerable in adults with active CD;

2) XN will improve biomarkers and improve the Crohn's Disease Activity Index (CDAI) an activity index of CD activity;

3) We can identify a biological signature(s) of XN through its metabolic byproducts in blood, urine, and stool as well as its effect on bile acid reabsorption; and

4) Specific biological signature(s) of XN exposure will uniquely contribute to changes in CD-associated disease activity indices.

To test these hypotheses and generate a conceptual model, we define four Specific Aims:

Protocol

- Aim 1. Determine the clinical safety and tolerability of xanthohumol in adults diagnosed with CD. We will determine the safety and tolerability of xanthohumol in adults diagnosed with CD over 8 weeks in a Phase 2 trial. The primary hypothesis is that in the XN arm, the number of participants with an adverse event or abnormal lab value will not be more than 50% higher than the number in the placebo group.
- Aim 2. Assess changes in levels of inflammation and symptom severity related to CD.

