Gut integrity and	Plasma concentrations of	ELISA will be used to measure
enterocyte damage	soluble CD14, intestinal	soluble markers of microbial
	fatty acid-binding protein,	translocation from the intestine
	and lipopolysaccharide-	
	binding protein by ELISA	
	Plasma endotoxin by	Plasma endotoxin by Limulus
	Limulus amebocyte lysate	amebocyte lysate assay will measure
	assay	the microbial translocation
	TLR2, TLR4 activation	HEK293 cells pre-transfected with
	by transfected HEK293	TLR4 and TLR2
	reporter cells	
Lipid metabolism	Lipidomics profiling	Liquid chromatography UPLC-QTOF

Primary Outcome: Clinical Safety/Cumulative Toxicology

Standard clinical Complete Blood Counts and toxicology panels including liver and renal function tests will be measured at each bi-weekly clinical visit. Values will be interpreted based on: new abnormal value, change since baseline, new emergency or alert values, and/or the emergence of new diagnostic concerns. All participants' labs will be reviewed by a clinical investigator, and any abnormal lab values meeting halting criteria will be recorded in the database.

Should a participant experience a severe or emergent event: 1. The AE and its severity will be documented; 2. The participant's medical provider will be notified and consulted; and, if unavailable, 3. The DSMB Chair ([name], MD, PhD; Division Chief of General Surgery, OHSU) will be consulted if the study team is unable to reach the participant's physicians.

Secondary Outcome: Fecal Calprotectin

Levels of calprotectin, a marker of CD, will be determined in stool samples using a commercial ELISA kit.

Secondary Outcome: Inflammatory markers

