A sample size of 12 per group provides 80% power to detect a 50% difference in proportions of participants between groups by chi2 test experiencing a laboratory abnormality or adverse event at a significance threshold of α =0.05. In addition, based on our preliminary trial data for change in TNF- α , and applying a 2-sided t-test of means, n=24 allows for n=12 per arm and provides >90% power, at a significance threshold α =0.05, to detect a mean change of -0.5 =/- 0.25 pg/ml in XN-treated participants with CD, based on an estimated mean change of 0.1 +/- 0.25 pg/ml from placebo. Will we randomize up to 32 participants to allow for attrition up to 25% [resulting in a final sample of at least n=24/arm.

Based on our preliminary trial data for change in TNF- α , and applying a 2-sided t-test of means, n=24 allows for n=12 per arm and provides >90% power, at a significance threshold α =0.05, to detect a mean change of -0.5 =/- 0.25 pg/ml in XN-treated participants with CD, based on an estimated mean change of 0.1 +/- 0.25 pg/ml from placebo. Will we randomize up to 32 participants to allow for attrition up to 25% [though we had <10% attrition in our previous trial in this population] resulting in a final sample of at least n=24/arm.

15 Recruitment

Participants will be recruited from the region via posted fliers and the NUNM clinic via posted fliers and IRB-approved mailings to current patients. Members of the study team will present information about study participation to CD support and community groups and set out flyers for attendees to pick up. In addition, we will use Craigslist and social media (i.e. Facebook and Instagram) as well as the NUNM weekly newsletter. Candidates from the community would

simply respond to a dedicated study telephone line or email, and express their interest, and are then contacted by a Study Coordinator.

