Laboratory measures (including red blood cell count, white blood cell count, hematocrit (%), hemoglobin, mean corpuscular volume, AST, ALT, creatinine-estimated glomerular filtration rate (eGFR), blood urea nitrogen (BUN), and creatinine) will be analyzed by first assessing descriptive statistics including mean, median and standard deviation. All distributions will be tested for skew and transformed (e.g., natural log transformed) as needed to reduce the influence of skew in subsequent analyses. All parameters will be evaluated by formally comparing means from baseline

Protocol

to each time point by unpaired, 2-sided t-tests, as well as for trends over time by applying linear mixed ANOVA models with time point as a repeated factor.

As an element of the evaluation for safety of the intervention, the % laboratory newly abnormal (for values within the clinically normal range at baseline) per clinical laboratory reference ranges for each lab parameter will be reported at each 2-week time point and the % compared between XN and placebo groups by Fisher's exact test.

Assessment for changes in the distribution of each lab parameter will be performed by presenting means and confidence intervals (CI) for the change in each group, as well as the mean CI for the difference between groups; significance will be tested using 2-sided, unpaired t-tests (or, if inspection of distributions indicates strong non-normality, with a non-parametric Wilcoxon signed rank test) of the mean values for XN compared to placebo.

Assessment for overall *increases* or *decreases* in parameters of interest will be tested for linear trends of the means by linear mixed ANOVA with time point as a repeated factor, which may be suggestive of evidence for cumulative toxicity if trending in a clinical deleterious direction.

Analysis of inflammatory cytokines, gut permeability biomarkers, and endotoxemia:

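### The only categorical laboratory safety comparison cannot count worsening from an abnormal baseline, and Aim 1 does not say whether an abnormal value must be new or worsened

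*Protocol*

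**What the plan says.** The protocol describes the laboratory part of the primary safety outcome in several places.

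- **Section 20a, laboratory toxicology measures.** The categorical comparison reports "the % laboratory newly abnormal (for values within the clinically normal range at baseline) per clinical laboratory reference ranges for each lab parameter" at each two-week visit and compares the arms by Fisher's exact test. It is introduced with the words "As an element of the evaluation for safety of the intervention". The same section also gives changes with confidence intervals, between-arm tests of means and linear mixed models for cumulative toxicity. None of these is restricted to participants normal at baseline.
- **Section 7, Aim 1.** The primary hypothesis is that in the xanthohumol arm "the number of participants with an adverse event or abnormal lab value will not be more than 50% higher" than in the placebo arm. It does not require the value to be new or worse than baseline.
- **Section 14.** The sample size refers to participants "experiencing a laboratory abnormality or adverse event".
- **Section 12, primary outcome.** Laboratory values are to be interpreted by whether they are newly abnormal, by change from baseline, by new alert values and by new diagnostic concerns.
- **Section 10.** No criterion excludes abnormal baseline laboratory values.
- **Section 6a.** The consequences of Crohn's disease are said to include "micronutrient malabsorption, iron deficiency anemia, increased risk of colon cancer, and unintended weight loss".

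**The concern.** Two rules for the laboratory event sit side by side, and each has a weakness in this population.

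Under section 20a, a participant who enters with low hemoglobin leaves both the numerator and the denominator of the hemoglobin comparison. A small step across the reference limit by someone normal at baseline is an event. A large further fall in someone already below the limit is not. Section 12 names change from baseline as a basis for interpretation, but no participant-level event in 20a uses it.

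Under Aim 1 taken at its word, the opposite happens. An abnormality present at entry and unchanged throughout makes the participant an event in either arm. Such events are unrelated to treatment, so they add about equally to both arms and dilute the ratio on which the hypothesis is stated. Dilution favors a finding of safety, because the hypothesis is met when the ratio is small.

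Safety is the primary aim of a 32-participant trial, so what counts as a laboratory event should be the same in the hypothesis, the sample size and the analysis.

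**Working it through.** **The plan's own figure.** Section 14 states: "A sample size of 12 per group provides 80% power to detect a 50% difference in proportions of participants between groups by chi2 test". The control rate is not given. For a 50-point absolute difference, the two-sided pooled normal approximation with 12 per arm gives 80.2% power at 5% v 55%, 76.2% at 10% v 60% and 71.4% at 25% v 75%. The stated 80% therefore reproduces at a control rate near 5% (or, by symmetry, 45%). The attrition arithmetic also reproduces: 24 / (1 − 0.25) = 32. Neither figure settles which laboratory event is meant.

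**Check 1: what 20a can count.** For one parameter there are three kinds of participant.

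| Baseline | On study | Event in the Fisher comparison? | In the mean-change and trend analyses? |
|---|---|---|---|
| Normal | Becomes abnormal | Yes | Yes |
| Abnormal | Stable | No, not in the denominator | Yes |
| Abnormal | Worsens | No, not in the denominator | Yes |

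The second and third rows cannot be told apart in the categorical comparison. That is the gap. It applies per parameter: someone anemic at baseline can still be an event for ALT.

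**Check 2: what Aim 1 does if read literally.** Inputs, all assumed because the protocol gives none of them:

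- q, the share of participants with a baseline abnormality that persists, equal in both arms and always counted as an event;
- new-event rates among the remaining participants of 20% on placebo and 40% on xanthohumol, a true doubling.

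Observed rate = q + (1 − q) × new-event rate, and the ratio is xanthohumol over placebo.

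| q | Placebo | Xanthohumol | Ratio |
|---|---|---|---|
| 0% | 0.20 | 0.40 | 2.00 |
| 10% | 0.10 + 0.90 × 0.20 = 0.28 | 0.10 + 0.90 × 0.40 = 0.46 | 1.64 |
| 20% | 0.20 + 0.80 × 0.20 = 0.36 | 0.20 + 0.80 × 0.40 = 0.52 | 1.44 |
| 30% | 0.30 + 0.70 × 0.20 = 0.44 | 0.30 + 0.70 × 0.40 = 0.58 | 1.32 |
| 40% | 0.40 + 0.60 × 0.20 = 0.52 | 0.40 + 0.60 × 0.40 = 0.64 | 1.23 |

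The ratio equals Aim 1's limit of 1.5 when q + 0.4(1 − q) = 1.5 × [q + 0.2(1 − q)]. This reduces to 0.1(1 − q) = 0.5q, so q = 1/6, or about 17%. Above that share, a true doubling has an expected ratio inside the limit. Because Aim 1 pools all parameters, q is the share abnormal on at least one of them, which cannot be smaller than the share for any single parameter.

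**The case against.** The case against a broad reading is strong, and most of it stands.

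- **A reader might infer that worsening in these participants is never assessed.** The documents do not support this. Section 20a calls the newly-abnormal table one element. Its mean-change and trend analyses include everyone, section 12 lists change from baseline and new alert values, a clinical investigator reviews all laboratory results, and section 11b withdraws participants for critical values. The gap is confined to the categorical arm comparison.
- **A reader might take it as fact that Aim 1 counts stable abnormality.** That is only the literal reading of an unqualified phrase. The section 14 wording can mean onset during the study, and section 11b speaks of new abnormal values. What stands is that Aim 1 leaves the matter open.
- **A reader might see a third event definition in section 12.** The sentence that "any abnormal lab values meeting halting criteria will be recorded in the database" is a recording instruction. It does not show that other results go unrecorded either: section 19 sends all study-visit data to the case report forms and then to REDCap.
- **The lost denominator is easy to overstate.** With no placebo events, Fisher's test needs five xanthohumol events to reach p < 0.05 at 12 per arm (2 × 792/42504 = 0.037) and also at 7 per arm (2 × 21/2002 = 0.021). Moving from 5/12 (42%) to 5/7 (71%) is the same five events over a denominator reduced by an assumed 40% abnormal share. It does not measure missed harm.
- **A better event definition will not make isolated deteriorations significant.** Two events against none at 12 per arm gives p = 2 × 66/276 = 0.48. Such cases are detected by individual review. The gain is that they appear in the comparison at all.
- **The baseline-abnormal share is unknown.** Section 6a reports an earlier study of a xanthohumol-containing formula in inflammatory bowel disease with mean laboratory values inside reference ranges. Means do not rule out individual abnormalities, but they lend no support to a high share.

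Detailed derivations may also sit in an SAP that is not shown. That does not answer the point that the protocol itself words the event differently in its primary hypothesis and its analysis.

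**Conclusion.** The point holds in a limited form. In section 20a the only categorical arm comparison of laboratory safety has no event for worsening from an abnormal baseline, in a population where the protocol itself makes some baseline abnormality plausible and does not exclude it. Aim 1 does not say whether an abnormal value must be new or worsened.

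The size depends on assumptions. With new-event rates of 20% v 40%, the literal Aim 1 rule brings the expected ratio below 1.5 once the persistently abnormal share passes about 17%. These are expected rates, before sampling error; other rates or a smaller share would change the result. It would be wrong to conclude that the safety evaluation as a whole is blind to harm in these participants, because the continuous analyses and individual review cover them. This is an inexpensive improvement to the primary endpoint definition; it does not invalidate the trial.

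**What to change.** Define one treatment-emergent laboratory event and use it in Aim 1, section 14 and section 20a. A participant has the event if a value becomes newly abnormal or worsens from the participant's own baseline in the harmful direction. Worsening could be, for example, an increase of at least one CTCAE v4.0 grade where a grade exists, and a pre-stated change for other analytes. Put all treated participants in the denominator, and keep the newly-abnormal table among participants normal at baseline as supportive.

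The change needs protocol wording and one more derived variable, with no extra samples or visits. Two things must be settled before unblinding: the thresholds for ungraded analytes, and an explicit statement that CTCAE grading applies to laboratory values. At present the protocol uses CTCAE only as the basis of the adverse event questionnaire (sections 18a and 22).

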The recently completed Phase 1 of XN at NUNM resulted no statistically significant differences in any mean laboratory values between XN vs. placebo groups at Closeout/Week 8 (all p values>0.10). At Closeout/Week 8, 2 laboratory parameters met halting criteria in Group B, including 1 mild anemia and 1 AST elevation. Notably, all lab abnormalities present at Closeout/Week 8 were resolved upon re-testing. There were no statistically significant differences in the frequency of any laboratory abnormalities between groups, at any timepoint in the trial (pvalues all>0.2). No participants discontinued their study intervention due to AEs. There were no "Grade 3/Severe" or FDA Serious AEs reported in either group. There were no apparent trends in incident AEs in either group over the time course of the trial. Additionally, investigators previously evaluated the effect of 12.5 mg per day of xanthohumol within a formula in adults with IBD, including Crohn's disease. Complete blood count and comprehensive metabolic panel data indicated no adverse changes; mean values were within normal laboratory reference ranges at all time points. All adverse events were non-serious and most were related to preexisting symptoms.¹⁵

There are no known toxicities for human subjects taking oral supplements containing XN. The general population is primarily exposed to XN through consumption of beer. A major brand beer contains about 0.5-1 mg prenylflavonoids (mainly XN and iso-XN) per liter and a bitter microbrew ale may contain as much as 4 mg of total prenylflavonoids.¹⁶ In Europe, a beer/beverage, containing 4 mg of XN per liter, has been on the market for several years without adverse effects having been reported by the consumers. Based on the available human data and the results from the above cited animal studies, we expect that the study participants will not develop adverse effects at the proposed dosage regimens during the 8-week exposure period.

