We aim to extend our preliminary findings related to potential application of XN as a therapeutic by testing its effects in a sample of human adults with CD. We will recruit 32 participants with CD, and randomize them to either 24 mg of XN plus rice protein, or a rice protein placebo for 8 weeks. The study drug will be identical to the preparation used in the Phase 1 trial that preceded this Phase 2 protocol, i.e., XN will be administered as 24 mg of a 99+% pure raw material provided by Hopsteiner USA (NY) combined with 288 mg of rice protein (California Natural Products, Lathrop, CA), 109.3 mg microcrystalline cellulose (Stauber USA, Fullerton, CA), 4.3 mg Aerosil®

Protocol

200 fumed silica (Vivion Inc., San Carlos, CA), and 4.3 mg magnesium stearate (Nitika Pharmaceutical Specialties, Maharashtra, India), and formulated into a capsule by Metagenics, Inc. (Gig Harbor, WA). XN has been combined with a rice protein carrier due to improved bioavailability.⁹

Our *primary working hypothesis* is that XN at the given dose will be safe and tolerable in adults with active CD. We will test this hypothesis by collecting blood samples at screening, baseline, and every two weeks to monitor changes in laboratory values including liver enzymes, renal function markers, and hematological markers. We anticipate very low frequency of treatment discontinuation due to adverse effects.

Our *working hypotheses* of Aims 2, 3, and the Exploratory Aim are that XN and its microbiotaderived metabolites may reduce inflammation and reduce biomarkers of barrier permeability in the inflamed gut. In order to test this hypothesis, we will collect blood, urine, and stool samples at baseline and every two weeks to monitor gut microbiome profiles and measure XN metabolite profiles. We will also measure fecal metabolome (including bile acid profiles) and lipidome profiles, as well as established fecal and plasma indicators of IBD severity, including fecal calprotectin and C-reactive protein. Because the actions of XN and its metabolites target specific abnormalities in CD, we hypothesize that the proposed studies will deliver a mechanism-based biological signature of XN exposure and its effect on CD mitigation.

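### Section 20a never tests or bounds the 50% safety margin in Aim 1: newly abnormal laboratory values are compared between arms only by Fisher tests of difference, and a non-significant Fisher result cannot support the primary hypothesis

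*Protocol*

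**What the plan says.** - **Primary hypothesis (Protocol section 7, Aim 1).** The number of XN participants with an adverse event or abnormal laboratory value "will not be more than 50% higher than the number in the placebo group". This is a per-participant composite with a relative margin of 1.5.
- **Primary outcome (section 12, Table 1).** Clinical safety and cumulative toxicology, measured by liver, renal and haematology tests.
- **How it is to be tested (section 6a).** "We will test this hypothesis by collecting blood samples at screening, baseline, and every two weeks to monitor changes in laboratory values".
- **Newly abnormal values (section 20a, laboratory toxicology measures).** For each parameter, the percentage newly abnormal "will be reported at each 2-week time point and the % compared between XN and placebo groups by Fisher's exact test". The denominator is restricted: "for values within the clinically normal range at baseline".
- **Means (section 20a).** Confidence intervals are given for the change in each group, "as well as the mean CI for the difference between groups", and "significance will be tested using 2-sided, unpaired t-tests". Linear mixed models look for trends in means, "which may be suggestive of evidence for cumulative toxicity if trending in a clinical deleterious direction".
- **Sample size (section 14).** Twelve per group is said to give 80% power for a 50% difference in the proportion with a laboratory abnormality or adverse event, by chi-square test at alpha 0.05. Up to 32 are randomised to allow for 25% attrition.

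**The concern.** Aim 1 is a claim that excess harm is limited, and it names the limit. Supporting it takes an estimate of the excess and an upper bound set against that limit. Section 20a supplies neither for the composite. For newly abnormal values it supplies only tests of no difference, one per parameter and visit.

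With 12 to 16 participants per arm, such a test will often be non-significant whether or not there is an excess. At stake is the primary conclusion: the specified analysis could end in a table of non-significant p-values that leaves the Aim 1 question unanswered. The protocol's Phase 1 summary in section 6a shows that such a statement can enter a safety account: "There were no statistically significant differences in the frequency of any laboratory abnormalities between groups, at any timepoint in the trial".

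**Working it through.** **Inputs.** Randomised: 32, taken as 16 per arm (1:1 assumed). Completing: 32 × (1 − 0.25) = 24, or 12 per arm. Alpha 0.05. Fisher's test is taken as two-sided, because section 20a does not say. The protocol gives no event rates, so the counts below are illustrations.

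**1. The plan's own power figure.** Normal approximation: power = Φ[(d − 1.96·se0)/se1].
- Read as an absolute 50-point difference, 5% v 55% with n=12: se0 = √(0.30 × 0.70 × 2/12) = 0.187; se1 = √[(0.05 × 0.95 + 0.55 × 0.45)/12] = 0.157; (0.50 − 0.367)/0.157 = 0.85; power 80%. The figure reproduces. At 25% v 75% it is 71%.
- Read as a relative 50% increase, which is the scale of Aim 1: 8% at 20% v 30%, 16% at 40% v 60%, 24% at 50% v 75%.

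So section 14 sizes a test to detect a very large absolute difference. It does not size a demonstration that the ratio is below 1.5.

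**2. Fisher's test with equal at-risk counts.** With x events on XN and none on placebo, two-sided p = 2·C(n,x)/C(2n,x).

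| XN v placebo | Calculation | p |
|---|---|---|
| 4/12 v 0/12 | 2 × 495/10,626 | 0.093 |
| 4/16 v 0/16 | 2 × 1,820/35,960 | 0.101 |
| 2/16 v 0/16 | 2 × 120/496 | 0.48 |

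A 33% or 25% rate of new abnormality on XN against none on placebo is therefore non-significant at a visit.

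**3. What an interval would show.** For 2/16 v 0/16 the difference is 12.5 points. The Wilson 95% limits are 3.5% to 36.0% for 2/16 and 0% to 19.4% for 0/16. Newcombe's method gives:
- lower = 0.125 − √[(0.125 − 0.035)² + 0.194²] = −0.09
- upper = 0.125 + √[(0.360 − 0.125)² + 0²] = 0.36

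The same data that give p=0.48 are compatible with an excess of about 36 percentage points. For 4 v 0 the Newcombe interval is 2% to 61% at 12 per arm and 1% to 50% at 16 per arm.

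**4. What the margin would require.** Suppose both arms have exactly the same number x with the Aim 1 composite. The log-method upper 95% limit of the ratio is exp(1.96·√(2/x − 2/n)).
- 8/16 in each arm: √(0.250 − 0.125) = 0.354; upper limit 2.0.
- 6/12 in each arm: √(0.333 − 0.167) = 0.408; upper limit 2.2.
- 12/16 in each arm: √(0.1667 − 0.125) = 0.204; upper limit 1.49.

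Even identical arms exclude 1.5 only when about three quarters or more have an event. At such rates the margin says little: once the placebo proportion exceeds 1/1.5 = 67%, a 50% excess is arithmetically impossible. This is why the risk difference is needed beside the ratio.

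**The case against.** The strongest reply is that Fisher's test is described as one element of the safety evaluation. Section 20a also fits trend models for means, section 12 has a clinical investigator review all laboratory results, and sections 11b and 21 provide withdrawal for critical values, monitoring-board review and a halting rule. None of these needs p<0.05. That stands as an account of participant protection. It does not fill the gap: trend models address means, the halting rule pools both arms, and none of them estimates the between-arm excess that Aim 1 refers to.

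Several stronger readings are tempting, and the document does not support them.
- A reader might infer that the protocol has no safety margin. Aim 1 states one; the fault is that section 20a does not use it.
- A reader might infer that no comparison carries a bound. Between-group intervals are planned for means; they are missing only for the percentage newly abnormal.
- A reader might infer that 4 v 0 is always non-significant. Because the denominator excludes participants abnormal at baseline, at-risk counts can differ: 4/15 v 0/16 gives p=0.043 and 4/12 v 0/13 gives p=0.039.
- A reader might infer that testing by visit hides a signal that a cumulative count would catch. The protocol runs four visits, not one. In simulations with 12 to 16 per arm and assumed within-person correlation 0.2 to 0.5, 10% v 30% per visit gave at least one significant visit in 25-47% of trials, against 23-44% for the cumulative count. For 5% v 20% the figures were 12-31% and 18-40%. The any-visit figures are unadjusted for multiplicity. The case for counting each participant once is that it matches Aim 1, not that it gains power.
- A reader might infer that the investigators will declare XN safe on p>0.05. No sentence says so, and the Phase 1 summary also reports halting-criteria values, resolution on re-testing and the absence of serious events.

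Interval methods for proportions are often left to a statistical analysis plan, which is not shown. That is fair for the choice of method. Here, though, section 20a does state a between-arm rule for newly abnormal values, and it is of a kind that cannot answer the stated hypothesis.

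**Conclusion.** The point holds. Section 20a does not test or bound Aim 1's 50% margin, and its only between-arm comparison of newly abnormal laboratory values is a test of difference without an interval. The examples assume equal at-risk counts, 1:1 allocation and two-sided Fisher tests; the p-value for 4 v 0 falls below 0.05 when XN has slightly fewer at risk. The argument that non-significance cannot support the margin does not depend on those assumptions. The point is worth correcting before analysis because it concerns the primary hypothesis. It is a mismatch between hypothesis and analysis, and it does not show that participants are unprotected.

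**What to change.** In section 20a:

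1. For the Aim 1 composite (any adverse event or newly abnormal laboratory value, each participant counted once over weeks 2-8), report the XN/placebo ratio and the risk difference with 95% CIs. Compare the upper limit of the ratio with the protocol's own 1.5.
2. For each laboratory parameter, report the cumulative proportion newly abnormal at any visit in weeks 2-8 among those normal at baseline, as XN minus placebo with a 95% CI (Newcombe or exact).
3. Keep the per-visit percentages as descriptive, and state that a non-significant Fisher or t-test is not evidence of safety.

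The cost is wording and a few extra tables; visits, samples and participants are unchanged. The downside is that at 12 to 16 per arm the intervals will be wide. The trial will probably be unable to confirm the 50% margin, and the safety conclusion must be worded to say so.
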